##### (2) Secondary endpoints

The secondary endpoints include the followings:

- Sensitivity and specificity of CRI in differentiating altered peripheral perfusion determined with the CRT test. An optimal cutoff value for CRI will be determined with the ROC analysis for the primary endpoint.
- Pearson's or Spearman's correlation coefficient to assess the correlation between CRI and CRT values.

## 6.1.4 Methods and timing for assessing, recording and analyzing variables

The study team will perform assessments and measurements according to the following table:

Study Phase	Screening and registration	Study measurement at the bedside	Follow up
Review the inclusion and the exclusion criteria	X		
Informed consent/assent	X		
Assigning a unique study subject number	X		
Measurements for subject's basal characteristics		X	
Applying a SpO 2 sensor probe on the finger		X	
Measurements of CRI and CRT		X	
Adverse event assessment		X	
Medical record review for subject's basal characteristics			X

The study procedures listed in the table are described in the section 6.3 "Subjects", the section 6.4 "Procedures" and the section 13 "Informed consent process".

6.1.5 Equipment to be used for assessing, recording and analyzing variables and arrangements for monitoring maintenance and calibration

Equipment to be used in this study are described in the section 2 "Investigational device" and the section 6.4 "Procedures".

## 6.1.6 Any procedures for the replacement of subjects

No replacement condition is foreseen. Subjects who withdraws early will not be replaced as we plan to recruit up to 60 subjects to achieve at least 54 subjects to be analyzed as described in the section 7.2 "Sample size".

## 6.2 Investigational device(s) and comparator(s)

### 6.2.1 Description of the exposure to the investigational device(s) or comparator(s), if used

#### (1) Investigational device

The SpO2 sensor probe will be applied to a subject's fingertip.

#### (2) Comparator

The comparator is the visual CRT. There is no physical exposure for the CRT test.

### 6.2.2 Justification of the choice of comparator(s)

The comparator is the visual CRT, which is typically used to assess peripheral blood perfusion at the bedside. The CRI measurement has been developed to assess peripheral blood perfusion quantitatively as an alternative method to the visual CRT test. Therefore, comparisons between CRI and CRT need to be performed.

### 6.2.3 Other medical device or medication to be used during the clinical investigation

A standard patient monitor used in the ED will be used to collect information of patient's basal characteristics as listed below:

- Noninvasive blood pressure
- SpO2
- Pulse rate or heart rate
- Respiratory rate (if available)
- Body temperature

There is no medication to be used during the investigation.

### 6.2.4 Number of investigational devices to be used

- OLV-4201A Pulse Oximeter: 1 unit
- TL-271T3 SpO2 sensor probe: 1 sensor per subject

## 6.3 Subjects

### 6.3.1 Inclusion criteria for subject selection

Adult ED and ICU patients (both males and females without regard to diverse ethnic and racial backgrounds) who meet the following inclusion criteria will be recruited.

- Individuals 18 years of age or older
- Patients who present to the ED or who are admitted to the ICU of North Shore University Hospital (NSUH)

### 6.3.2 Exclusion criteria for subject selection

- Pregnant
- Prisoners
- Finger, hand or forearm anatomical anomaly or disease that may interfere with attaching a pulse oximeter sensor
- Patients' deemed clinically unstable by the clinical team

### 6.3.3 Criteria and procedures for subject withdrawal or discontinuation

All subjects are free to withdraw from the study at any time and for any reason. Subject safety will be monitored by the investigator who is a qualified ED physician. The primary safety concern is ensuring the patients are not distressed by the study procedures. All the procedures that subjects will receive are non-invasive, but if the subject reports any adverse effects during the course of the study, the investigators will immediately discontinue any procedures and remove any research instruments from the subject. Data collected up to the point of the subject's withdrawal will continue to be used and analyzed. No further data will be collected after the subject's withdrawal.

### 6.3.4 Point of enrollment

Adult patients who present to the ED of NSUH who meet the eligibility criteria will be recruited. Importantly, patients will only be approached who are physically available to participate in the study, as to not delay or interrupt the patient's care for recruitment. Informed consent will be obtained directly from the subject prior to all procedures. Then, a unique study subject number will be assigned, and the subject will be registered for this study.

### 6.3.5 Total expected duration of the clinical investigation

The duration of the study (including data collection and analysis) is approximately 1 year.

### 6.3.6 Expected duration of each subject's participation

Expected duration of each subject's participation is approximately 15 minutes.

### 6.3.7 Number of subjects required to be included in the clinical investigation

Total number of subjects is up to 60. Detail of the required sample size calculation is described in the section 7.2 "Sample size".

### 6.3.8 Estimated time needed to select this number (i.e. enrolment period)

The duration of subject enrollment is anticipated for 6 months.

### 6.3.9 Subject compensation

Each subject will receive a \$15 gift card as compensation for their participation in this study.

## 6.4 Procedures

### 6.4.1 All the clinical-investigation-related procedures that subjects undergo during the study

Adult ED patients aged 18 years and older will be recruited for this study. Informed consent will occur prior to the study enrollment. Patients will be assigned a unique study subject number. All data mentioned below will be recorded on paper forms. Raw data measured by the investigational device will be recorded digitally on a SD card inserted in the device. Data recorded on paper forms will be entered into REDCap so that it can be analyzed.

[figure not shown]
Patient's basal characteristics will be collected as shown below. Noninvasive blood pressure, SpO2, pulse rate, respiration rate and body temperature will be measured by a standard patient monitor used in the ED.

#### Obtained from medical record:

- Age
- Gender
- Race
- Height
- Body weight
- Past general medical history (diabetes mellitus, hypertension, smoking, heart disease, lung disease, others)
- Initial vital sign data (blood pressure, SpO2, pulse rate/heart rate, respiratory rate and body temperature)
- Core body temperature (if available)
- Red blood cell count (RBC), Hematocrit (Ht) and Hemoglobin (Hb) (if available)
- Lab data: Blood lactate levels, Cre/BUN and TP/Alb (if available)
- Primary diagnosis
- Disposition (Discharged home, admitted, left against medical advice, skilled nursing facility, other hospital, expired, unknown or other)
- Time of events (ED arrival, ED encounter, ED discharge and admission, etc.)

#### Obtained at the bedside:

- CRT
- CRI
- Noninvasive blood pressure
- SpO2
- Pulse rate or heart rate
- Respiratory rate (if available)
- Fitzpatrick skin tone scale

- Body temperature (axillary)
- Forearm and fingertip temperatures
- Room temperature

The surface temperature of the patient's hand will be measured by a non-contact infrared thermometer. To address the reliability of the subjective assessment of peripheral perfusion by the investigator, we will also measure forearm-to-fingertip skin temperature difference ( $T_{skin-diff}$ ), as well as central-to-fingertip temperature difference ( $T_c-diff$ ). The  $T_{skin-diff}$  will be obtained from the index/middle finger temperature and the temperature on the radial side of the forearm, midway between the elbow and the wrist.

The CRT and the CRI measurements will be conducted with following methods for each subject in a relaxed position (seated or lying down) with relaxed hands. The subject's most accessible hand (right or left) will be used. Each measurement will be performed alternately and will be repeated three times each for a total of six compressions per subject. If the subject is wearing nail polish, the investigator will measure CRI/CRT after removing the subject's nail polish. If the subject is wearing a ring on their finger, CRI/CRT will be measured after removing the ring(s).

#### **Visual CRT measurement using a stopwatch**

An investigator (an ED physician) will compress the fingertip of the subject's index or middle finger for five seconds, signaled by "start compression" and "release compression" beep sounds. When the fingertip is released from the compression, the investigator will begin the visual CRT measurement. The investigator will hold a stopwatch in the hand that does not perform the compression and use this stopwatch to measure CRT.

[figure not shown]
#### **CRI measurement by the investigational device**

The  $SpO_2$  sensor probe will be applied to either the index or middle fingertip of the same hand of the subject used in the CRT measurement, depending upon which fingertip was compressed in the CRT measurement. For example, if the index fingertip was used in the CRT measurement, then the sensor will be applied to the middle fingertip. With the sensor on it, the investigator will compress the subject's fingertip for five seconds by the investigator's finger as same way of the traditional CRT test. The sensor is flexible and thus, the investigator is able to compress the fingertip by compressing the sensor (Figure 2). The compression will be performed with signals from the device, and then the device will measure CRI.

**Figure 2:** Compression for the CRI measurement

The investigator will confirm the sensor probe is properly applied to the fingertip by measuring CRI and checking whether the shape of the CRI measurement waveform is proper. With proper application of the sensor probe, the measurement waveform is convex upward as shown in Figure 3. If the sensor probe is not properly applied, the investigator will replace the sensor probe.

**Figure 3:** Proper shape of the CRI measurement waveform

The investigator will be blinded from the measured value of the CRI measurement.

All subjects are free to withdraw from the study at any time and for any reason. The investigators will immediately discontinue any procedures and remove any research instruments from the subject. Data collected until the subject's point of withdrawal from the study will be analyzed. The estimated duration of the subject's participation is approximately 15 minutes in total.

#### 6.4.2 Activities performed by sponsor representatives (excluding monitoring)

There is no activity performed by sponsor representatives.

#### 6.4.3 Any known or foreseeable factors that may compromise the outcome of the clinical investigation or the interpretation of results

- Improper application of the sensor probe to the fingertip will cause inappropriate results of the measurement. The investigator will confirm the sensor probe is properly applied to the fingertip with the procedure described in the section 6.4.1. If the sensor probe is not properly applied, the investigator will replace the sensor probe.

## 6.5 Monitoring plan

Since this is a single site study, there is no plan for external site monitoring.

The principal investigator is tasked with ensuring the safety and data integrity of the study. The PI will continuously review the aggregate data to determine if any aspects of the study need to be changed or stopped. In addition, the PI will review any and all CIP deviations, adverse events, and unanticipated problems that may occur to determine their relatedness to the study, their severity, and whether they require study changes. Any unanticipated problems or instances of non-compliance will be reported to the IRB as per their reporting requirements. If any changes of CIP are needed, an investigator will submit a modification request to the IRB. CIP changes will not be implemented prior to IRB approval unless necessary to eliminate apparent immediate hazards to the research subjects. In such a case, the IRB will be promptly informed of the change following implementation.

The sponsor and/or representative may conduct periodic on-site monitoring visits during the course of the study, including study initiation and close-out to ensure appropriate documentation is present and completed. The investigator will permit study-related monitoring, audits, and inspections of all study related documents (e.g. source documents, regulatory documents, data collection instruments, study data etc.) by the IRB, the sponsor, government regulatory bodies, and compliance and quality assurance groups of the study site. The investigator will ensure the capability for inspections of applicable study-related facilities.

Participation as an investigator in this study implies acceptance of potential inspection by government regulatory authorities and applicable compliance and quality assurance offices of the study site.

## 7 Statistical considerations

### 7.1 Statistical design, method and analytical procedures

In order to assess the study aims and hypotheses, we will describe the study sample using descriptive statistics such as frequencies, proportions, means, standard deviations, 95% confidence intervals, medians, and interquartile ranges. The mean of the three repeated CRI and CRT measurements will be considered as the values for each subject.

The primary and secondary endpoints are described in the section 6.1.3. Receiver operator characteristic (ROC) curve analysis will be performed and area under the curve (AUC) will be calculated to demonstrate capability of CRI to predict altered peripheral perfusion determined with the CRT test. An optimal cutoff value for CRI will be determined with the ROC analysis and the sensitivity and the specificity in differentiating altered peripheral perfusion will be calculated. Pearson's, or Spearman's correlation coefficient will be calculated to assess the correlation between CRI and CRT values.

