**(2) Secondary endpoint(s)**

The secondary endpoints include the followings:

- Sensitivity and specificity of CRI in differentiating altered peripheral perfusion determined with the CRT test. An optimal cutoff value for CRI will be

determined with the ROC analysis for the primary endpoint.

- Pearson's or Spearman's correlation coefficient to assess the correlation between CRI and CRT values.

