#### 6.1.3 Primary and secondary endpoints

##### (1) Primary endpoint

The primary endpoint is the area under the curve (AUC) of the receiver operator characteristic (ROC) curve analysis on CRI values to predict the altered peripheral perfusion determined with the CRT test. A specific cutoff value for CRI has not yet been determined, then the AUC value will be used to summarize comprehensive capability of CRI to detect the altered peripheral perfusion. Procedures of the measurement of CRI and CRT, and statistical methods are described in the section 6.4 "Procedures" and the section 7 "Statistical considerations", respectively.

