## 7.2 Sample size

The primary endpoint of this study is an AUC of the ROC curve analysis on CRI values to predict altered peripheral perfusion determined with the CRT test. Sample size for subjects with altered peripheral perfusion required to obtain desired AUC is calculated with the following equation [9]:

$$n = \frac{Z_{\alpha/2}^2 \times V(AUC)}{d^2}$$

where,  $Z$  is the standard normal deviate determined with probability of type I error:  $\alpha$ ,  $d$  is the desired width of one-half of the confidence interval (CI), and  $V(AUC)$  is variance of AUC which is derived from the following equation [10]:

$$V(AUC) = (0.0099 \times e^{-a^2/2}) \times \{(5a^2 + 8) + (a^2 + 8)/\kappa\}$$

where,  $a = \varphi^{-1}(AUC) \times 1.414$ ;  $\varphi^{-1}$  is inverse of standard cumulative normal distribution; and  $\kappa$  is the ratio of the number of subjects without the altered peripheral perfusion to the number of subjects with the altered peripheral perfusion. Based upon our preliminary data:

- The prevalence of the subjects with altered peripheral perfusion is expected to be 30%, and then  $\kappa$  is 2.33.
- We hypothesize that the AUC will be 0.84, and then  $a = \varphi^{-1}(0.84) \times 1.414 = 1.406$ .

Therefore,  $V(AUC)$  can be calculated as follow:

$$V(AUC) = (0.0099 \times e^{-1.406^2/2}) \times \{(5 \times 1.406^2 + 8) + (1.406^2 + 8)/2.33\} = 0.0816$$

To achieve an AUC of at least 0.70 which is considered as fair [11], one-half of the CI:  $d$  should be 0.14 with the hypothesized AUC of 0.84. At the significance level of 5% (probability of type I error:  $\alpha = 0.05$ ), the number of subjects with altered peripheral perfusion is derived as:

$$n = \frac{Z_{\alpha/2}^2 \times V(AUC)}{d^2} = \frac{1.96^2 \times 0.0816}{0.14^2} = 15.99 \approx 16$$

The total number of required sample size given by  $n(1 + \kappa)$  is 54. Considering possible early withdrawals of subjects, we plan to recruit up to 60 subjects to achieve 54 evaluable subjects (10% of drop-out rate).

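### Sensitivity and specificity will be reported at a CRI cutoff picked as optimal in the same subjects, with no stated rule and no optimism correction, so they will tend to be too high

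*Combined protocol and SAP*

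**What the plan says.** Section 6.1.3 (1) explains that AUC is the primary endpoint because "A specific cutoff value for CRI has not yet been determined". Section 6.1.3 (2) and the synopsis then make this a secondary endpoint: "Sensitivity and specificity of CRI in differentiating altered peripheral perfusion determined with the CRT test". The cutoff comes from the same analysis: "An optimal cutoff value for CRI will be determined with the ROC analysis for the primary endpoint". Section 7.1 repeats it ("An optimal cutoff value for CRI will be determined with the ROC analysis and the sensitivity and the specificity"), and section 5.1.1 includes the same step in the text of the primary objective.

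Sections 7.1 to 7.13 do not say what makes a cutoff optimal or how ties are resolved. They contain no hold-out sample, cross-validation, bootstrap correction or exploratory label. Section 3.2 reports an AUC from the preliminary study but carries no CRI cutoff forward.

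**The concern.** A cutoff chosen because it performs best in a sample fits that sample's chance features as well as the real separation between groups. Sensitivity and specificity calculated at that cutoff in the same subjects are then too high on average, and more so when one group is small. Here sensitivity rests on about 16 subjects.

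The size of the bias depends mostly on the selection rule, which could be settled after the curve has been seen. This study would be the only source of both the cutoff and its performance, and section 17 foresees publication and use in FDA applications. Anyone planning the next CRI study would start from these figures.

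**Working it through.** **1. Planned counts (section 7.2).** Inputs: AUC 0.84, prevalence 30% (κ = 2.33), half-width d = 0.14, Z = 1.96.

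- a = Φ⁻¹(0.84) × 1.414 = 1.406
- V = 0.0099 × exp(−a²/2) × {(5a² + 8) + (a² + 8)/κ} = 0.0817 (plan: 0.0816)
- n = 1.96² × V / 0.14² = 16.00 (plan: 15.99, taken as 16)
- Total: 16 × 3.33 = 53.3, rounded up to 54; recruited: 54/0.9 = 60

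The plan's figures reproduce. Subjects without altered perfusion: 54 − 16 = 38.

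**2. Bias by cutoff rule.** Assumptions not in the documents: CRI is normal with equal SD in both groups, and the group means are set to give the stated AUC. In each of 100,000 simulated datasets (16 vs 38) the cutoff is chosen by the rule, taking the middle of tied cutoffs. Apparent sensitivity/specificity is compared with the true values at that same cutoff. Results at AUC 0.84, in percent; differences come from unrounded values:

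| What optimal could mean | Reported | True at chosen cutoff | Overstatement (points) |
|---|---|---|---|
| Maximum Youden index | 81.9/78.9 | 73.4/75.4 | 8.6/3.5 |
| Maximum sensitivity × specificity | 81.4/79.2 | 73.5/76.0 | 7.9/3.2 |
| Maximum overall accuracy | 63.1/91.6 | 55.6/88.0 | 7.4/3.6 |
| Closest to the ROC corner | 80.2/79.5 | 73.5/76.7 | 6.8/2.8 |
| Sensitivity = specificity | 76.0/75.8 | 75.4/75.5 | 0.6/0.2 |

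The Youden index itself averages 0.609 reported against 0.488 true. Even the best possible cutoff under these assumptions has a true index of only 0.518 (75.9% for both measures). For the last rule, a different tie rule gave 1.1/0.5.

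**3. Sensitivity to the assumptions** (overstatement in points, sensitivity/specificity):

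| Scenario | Youden | Corner | Sensitivity = specificity |
|---|---|---|---|
| AUC 0.70 | 10.3/4.3 | 7.6/3.2 | 0.5/0.2 |
| AUC 0.90 | 7.6/3.1 | 6.2/2.5 | 0.8/0.3 |
| AUC 0.84, 11 vs 43 | 11.4/2.8 | – | – |
| AUC 0.84, 22 vs 32 | 6.6/4.4 | – | – |
| AUC 0.84, SD in positives × 1.5 | 8.0/3.3 | – | – |
| AUC 0.84, SD in positives × 2 | 7.2/3.0 | – | – |

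Replacing the two-group model with a bivariate normal for CRI and CRT (r = 0.723 from section 3.2, 30% positive, N = 54) again gives about 8.6/3.5 under Youden. With 160 vs 380 subjects the optimism in the Youden index falls to 0.542 − 0.511 = 0.031.

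**4. Bias against random error.** Under Youden at AUC 0.84 the reported values vary between trials with an SD of about 12 points each. Part of that is genuine movement of the operating point. For sensitivity, the error around the true value at the chosen cutoff has RMSE 0.124 and bias 0.086, so its SD is √(0.124² − 0.086²) = 0.089. The bias in sensitivity is therefore about as large as its random error.

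**5. Corrections** (Youden rule, AUC 0.84, first 3,000 of the same datasets; 200 resamples stratified by group, or 10 × 8-fold stratified cross-validation):

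| | Apparent | Bootstrap | Cross-validation |
|---|---|---|---|
| Mean Youden index (true 0.489) | 0.609 | 0.532 | 0.485 |
| RMSE, Youden index | 0.158 | 0.126 | 0.142 |
| RMSE, sensitivity | 0.124 | 0.105 | 0.124 |
| RMSE, specificity | 0.072 | 0.067 | 0.087 |

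The bootstrap removes (0.609 − 0.532)/(0.609 − 0.489) = 64% of the bias. The share is similar at AUC 0.70 (0.406 to 0.314, true 0.260: 63%) and for the corner rule at AUC 0.84 (0.597 to 0.535, true 0.503: 66%).

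**The case against.** The strongest reply is that little hangs on these figures. AUC was made primary precisely because no cutoff exists. The pass criterion in section 7.5, the sample size and the CRI–CRT correlation use no CRI cutoff. Sensitivity and specificity have no target or decision rule, and section 5.3 limits CRI to clinical research rather than diagnosis. Deriving a first cutoff is normal early work. All of this stands, and it limits the seriousness of the point. It does not make the reported figures right, and the plan nowhere marks them as exploratory.

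Second, the size depends on a rule the plan does not name, and under sensitivity = specificity there is almost nothing to correct. That is true. A final report naming the rule would also tell the reader which case applies, but not that the rule was fixed before the curve was seen.

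Third, the corrections are imperfect. The bootstrap leaves about a third of the bias. Cross-validation removes nearly all of it on average, but does not improve RMSE for sensitivity and worsens it for specificity. This argues for the bootstrap, described as a partial correction. It does not argue for reporting the apparent values alone, whose RMSE is higher than the bootstrap's for both measures.

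**Conclusion.** The concern holds. The same subjects supply the cutoff and its accuracy, the selection rule is open, and no correction or caveat is planned. At 16 vs 38 and AUC 0.84, rules that maximise apparent accuracy overstate sensitivity by about 7 to 9 points and specificity by about 3 to 4 on average; a sensitivity = specificity rule overstates by about 1 point or less. These sizes rest on normally distributed CRI and on the plan's 30% prevalence, which comes from preliminary data; the preliminary study in section 3.2 enrolled ED patients only, whereas ICU patients are now included. The upward direction was the same in every scenario examined, but it is an average, and a single trial can still come out low. The point should be addressed; it does not threaten the primary conclusion.

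**What to change.** Amend section 7.1, section 6.1.3 and the synopsis as follows:

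1. Name the cutoff rule and the tie rule before the data are analysed.
2. Report optimism-corrected sensitivity and specificity beside the apparent values. A suitable method is a bootstrap that resamples subjects with and without altered perfusion separately and re-selects the cutoff in every resample; state that the correction is partial. Repeated cross-validation is an alternative, with less bias and more noise. If a sensitivity = specificity rule is fixed, the correction will change little.
3. Label the cutoff and its sensitivity and specificity as exploratory until validated in new subjects. Any confidence interval given for them should account for the cutoff selection and be described as approximate.

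The cost is a short paragraph, a few lines of code and slightly less favourable figures. Fixing the rule also gives up the freedom to choose the operating point after seeing the curve. No extra subjects or procedures are needed, and the primary endpoint and its criterion do not change.
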